Dialysate is generated during dialysis from two concentrates (acid concentrate and bicarbonate concentrate) mixed with treated water. When used, citrate is provided in the acid concentrate. For this study, patients will undergo hemodialysis using a citrate acid concentrate (Citrasate; Fresenius Medical Care) or non-citrate acid concentrate (Naturallyte; Fresenius Medical Care), each for one year in a cross-over study. Both acid concentrates are approved for this use by the FDA and will be used according to standard procedures without altered dialysis machine settings. Citrasate is the acid concentrate currently in use at all Emory Dialysis units and the final dialysate is pumped to each patient station from a central location. Therefore, the study intervention will be the use of Naturallyte instead of Citrasate. The Naturallyte will be ordered and stored by dialysis personnel and used by the dialysis technicians or nurses. It will be provided locally at each station as individual containers (the dialyzers are designed to use either centrally or locally supplied dialysate) so there is no risk of non-study patients receiving dialysate from Naturallyte acid concentrate.

6. Procedures Involved

Female hemodialysis patients will undergo screening mammography and those who have BAC will be enrolled. This will be a cross-over study in which half the patients will continue with citrate dialysis and the other half will be switched to non-citrate dialysis. After one year, the patients will be switch to the other dialysis. Dialysis treatments are performed 3 times per week. Mammograms will performed at 6, 12, 18 and 24 months at Emory Healthcare facilities. Patients will have monthly blood draws as part of their routine clinical care and are seen on a weekly basis by the attending nephrologist or nurse practitioner. Data to be collected during the study include:

- measurements of BAC on the mammograms (every 6 months). The mammograms will be interpreted by radiologists.
- plasma citrate, magnesium, and ionized calcium levels immediately before and after dialysis (every 6 months). These will be obtained during routine clinical blood draws and represent an insignificant amount of extra blood.
- routine blood chemistries (monthly as part of clinical protocol)

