Data analysis. Rate of BAC progression will be calculated by linear regression of 3 mammograms in each treatment arm: 0, 6, 12 months vs. 12, 18, 24 months. Comparison will be by paired t-testing (or Wilcoxon test in the case of nonparametric distribution). Also, the proportion of women with a decrease in BAC rate during citrate dialysis will be examined by Fisher's Exact Test. Laboratory values and dialysis parameters will be compared in patients with and without a decrease in BAC rate.

Study size. The goal is a final cohort of 50. The attrition rate among females at Emory Dialysis over the past 9 years has averaged 9.2% per year. However, this is an over-estimate since it likely includes women who would not have qualified for the study. Using a drop-out rate of 10% per year, a starting sample of 62 will be needed. Based on previous data 24, 60% of HD patients will have baseline calcification. Thus, 103 will need to be recruited and screened for BAC.

Power. Our previous studies comparing BAC rates calculated from the first 3 and last 3 mammograms (the study design for this proposal) yielded a standard deviation of 11.9 mm/breast/y. Using this value and the median BAC rate in HD patients of 20.1 mm/breast/y 27, a cohort of 47 women would provide 80% power to detect a 25% change in rate at $p=0.05$. In two longitudinal studies calculating rates from just two mammograms, we were able to detect a 78% decrease in the rate of BAC after stopping warfarin at $p=0.02$ in just 13 patients 28 and a 90% decrease after kidney transplantation in only 9 patients (unpublished data).

Subject availability. There are currently 300 female in-center HD patients within Emory Dialysis and it is estimated that at least 80% or 240 will qualify for screening. Therefore, a recruitment rate of 43% will be required. Describe the data analysis plan, including any statistical procedures or power analysis.

Data management. Data collected will be mammograms, research blood assays (citrate, magnesium, ionized calcium), clinical blood assays, and dialysis parameters. All data/specimens will be handled clinically except for samples for research assays, which will be transported to the P.I.'s laboratory by the research coordinator. Mammograms

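### The laboratory and dialysis comparison splits women by whether BAC rate fell, and so discards the size of each woman's change; at the design values this costs about 40% of the information in an exploratory analysis

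*Combined protocol and SAP*

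**What the plan says.** All of this is in the combined protocol and SAP.

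- **Outcome.** Section 18, Data analysis, defines a slope per woman per period (times in months): "Rate of BAC progression will be calculated by linear regression of 3 mammograms in each treatment arm: 0, 6, 12 months vs. 12, 18, 24". The difference between her two slopes is a continuous number.
- **Primary comparison.** This uses the size of that difference: "Comparison will be by paired t-testing (or Wilcoxon test in the case of nonparametric distribution").
- **Predictor comparison.** The same paragraph ends: "Laboratory values and dialysis parameters will be compared in patients with and without a decrease in BAC rate". It names no test, gives no reason for cutting at zero, and does not say which laboratory values are meant (baseline, on-treatment, or change between periods).
- **Data collected for it.** Section 6 lists "plasma citrate, magnesium, and ionized calcium levels immediately before and after dialysis (every 6 months"), together with monthly routine chemistries and dialysis parameters captured at each session.
- **Planning values.** Section 18, Power, uses an SD ("yielded a standard deviation of 11.9 mm/breast/y") and "the median BAC rate in HD patients of 20.1 mm/breast/y", and states that "a cohort of 47 women would provide 80% power to detect a 25% change in rate at $p=0.05". The Study size paragraph adds: "The goal is a final cohort of 50".

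No regression or correlation on the size of the rate change is planned anywhere.

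**The concern.** Under the split, a woman whose rate falls by 1 mm/breast/y counts the same as one whose rate falls by 30. A woman near zero is placed in one group or the other largely by noise in two three-point slopes. The planned SD of 11.9 is more than twice the planned mean change of 5.025, so many women will lie near the cut.

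This sentence is the only place where the plan ties the measured citrate, magnesium and ionized calcium to calcification. Two things are at stake: the chance of seeing a real association with about 50 women, and the risk that the two groups are later described as responders and non-responders when much of the sorting is random.

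**Working it through.** **Inputs.** From section 18: reference rate 20.1 mm/breast/y, change to detect 25%, SD 11.9 mm/breast/y, alpha 0.05, power 80%, stated n of 47, final cohort 50. Assumed: a two-sided test (sidedness is not stated), an approximately normal change, and weak linear associations.

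**Step 1: reproduce the plan's figure.** The difference to detect is 0.25 × 20.1 = 5.025, and 5.025/11.9 = 0.422.

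- Normal approximation for a paired comparison: n = ((1.960 + 0.842) × 11.9/5.025)² = 44.0, so 45.
- Noncentral t: 46 women give power 0.800, 47 give 0.809 and 50 give 0.833.

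The stated 47 reproduces to within 2 women. One-sided testing would need 35, and two independent groups would need 89 per arm; neither matches. Reading 11.9 as the SD of the within-woman difference therefore fits the plan.

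**Step 2: information kept by the split.** For a weak linear association with a normal outcome cut at zero, the efficiency relative to the continuous analysis is φ(c)² / [P(1 − P)], where c = mean/SD and P = Φ(c).

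- c = 0.422, P = 0.664, φ(c) = 0.365, P(1 − P) = 0.223.
- Efficiency = 0.365²/0.223 = 0.597. Correlations shrink by √0.597 = 0.77.
- 50 × 0.597 = 29.8 women.

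The result depends on the true mean effect:

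| True change in rate | Share with a decrease | Efficiency | Loss | Equivalent of 50 women |
|---|---|---|---|---|
| none | 0.500 | 0.637 | 36% | 31.8 |
| 10% | 0.567 | 0.630 | 37% | 31.5 |
| 25% (design) | 0.664 | 0.597 | 40% | 29.8 |
| 40% | 0.750 | 0.538 | 46% | 26.9 |
| 50% | 0.801 | 0.489 | 51% | 24.4 |

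**Step 3: power at n = 50.** Simulation with 40,000 runs and normal data at the design mean and SD, comparing a Pearson correlation with a two-group t-test on the split. The true correlations are illustrative assumptions; the documents give none.

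| True correlation | Continuous | Split |
|---|---|---|
| 0.3 | 57% | 37% |
| 0.4 | 83% | 60% |
| 0.5 | 97% | 82% |

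**Step 4: heavier tails.** With the same mean and SD, a correlation of 0.4 and residuals from a t distribution with 3 degrees of freedom, Pearson has about 86 to 87% power and the split 82 to 83%. A rank correlation has about 95%. With Laplace residuals, Pearson has 83% and the split 74%.

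**Step 5: what the labels mean.** If every woman had the same true change of 5.025 and the SD were all noise, 1 − 0.664 = 34% would still be labelled as having no decrease. With no effect at all, 50% would be labelled as having a decrease.

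**Step 6: direction of the predictor.** Suppose the outcome is non-citrate minus citrate but the predictor is taken as period 2 minus period 1. The predictor's sign then flips between the two sequences, and a sequence main effect does not repair this. In simulation, a true correlation of 0.4 then gives an average slope of about zero and about 6% power. The direction has to be written into the plan.

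**The case against.** The case for leaving the sentence alone has several parts.

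- **It is a supporting comparison.** Section 4 names one endpoint, the secondary-objective field in section 1 is empty, and no alpha, power or claim is attached to this sentence. That stands. No conclusion about citrate from the primary test changes. A reader might call this the trial's evidence on mechanism, but the documents do not present it as such.
- **The 40% is not a fixed cost.** A reader might infer that the split always loses 40%. It does so only for a roughly normal change at the 25% effect. The plan itself foresees non-normal data through its Wilcoxon fallback. With t residuals on 3 degrees of freedom, ordinary regression has little advantage, and in the weak-association limit the split is slightly more efficient (1.10). That stands as a limit on the figure, but in the simulated case a rank correlation restores a clear advantage, so the case for keeping magnitude survives.
- **The plan may use the crossover data.** A reader might infer that within-woman laboratory changes are ignored. Section 18 does not say which values are compared, and comparing changes between the two groups would fit its wording. This is under-specification, not a demonstrated error.
- **Chance labelling does not by itself favour regression.** If all women share one true effect, there is no variation in response for any method to explain, and slope noise stays in the continuous difference too. That stands. Step 5 is a warning against responder language, not evidence for the fix.

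**Conclusion.** The point holds at modest weight. The plan obtains a continuous change for each woman and uses only its sign when relating it to laboratory values and dialysis parameters. With a roughly normal change at the design mean and SD, and weak linear associations, about 60% of the information is kept. The loss is about 36% with no mean effect, rises above 40% if the effect exceeds 25%, and can be much smaller relative to ordinary regression when tails are heavy. The power figures also rest on assumed correlations.

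A reader might go further and conclude that the trial's main result is weakened. The documents do not support that: the paired primary test uses the full rate difference.

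**What to change.** Replace the sentence in section 18 with an exploratory analysis along these lines:

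- **Outcome:** each woman's rate difference, non-citrate minus citrate, in mm/breast/y, kept continuous.
- **Predictors:** her change in each quantitative laboratory value or dialysis parameter, also non-citrate minus citrate, and separately her baseline level. State which visits supply each value. Section 6 does not say whether the six-monthly research assays start at month 0; if they do not, baseline analyses are limited to the routinely captured data.
- **Model:** linear regression with a sequence term, reporting slopes with 95% confidence intervals. Add a rank correlation when the change is not normal.
- **Exclusions and categories:** leave out parameters fixed by treatment, such as the citrate content of the dialysate, which changes identically for every woman. Summarise categorical items such as medications suitably.
- **Labelling:** call the results exploratory, since there are many predictors and about 50 women. Keep the decrease/no-decrease table as description only.

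The cost is a short edit to the analysis text. It needs no extra patients, visits, assays or mammograms, so this is a free improvement.

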- dialysis parameters: dialysate composition, anticoagulation, body weight, ultrafiltration volume, vital signs, medications, and dialysis adequacy (automatically captured for each dialysis session in the clinical database)

Minimizing risk: Patients are routinely monitored continuously during dialysis by staff nurses and/or technicians. In addition they will be seen by nurse practitioners weekly and by attending nephrologists monthly.

Drug/device use: Naturalyte acid concentrate, which is FDA-approved for this use.

Source records/data collection: All dialysis data is automatically stored in the clinical database. Mammograms are stored in the Emory Healthcare PACS system.

Long-term follow-up: none.

7. Data and Specimen Banking

No specimens will be collected. Data will be available only to the PI and study coordinator. It will only be released to others in a de-identified form.

8. Sharing of Results with Participants

Results of the mammograms (other than the vascular calcification) will be entered in the medical record, shared with the patients, and reported to the attending nephrologist. Any suspicious findings on mammograms will be pursued per normal clinical protocol by the Breast Imaging Center, which includes contacting and educating the patient and arranging appropriate follow-up (repeat diagnostic mammograms, ultrasound, biopsy).

9. Study Timelines

Duration of an individual participant's participation in the study: 2 years.

Duration anticipated to enroll all study participants: 2 months.

Estimated date for the investigators to complete this study (complete primary analyses): 27 months.

10. Inclusion and Exclusion Criteria

Describe how individuals will be screened for eligibility: mammogram.

Inclusion criteria: adult female hemodialysis patients with BAC on mammograms.

Exclusion criteria: current warfarin use, severe hyperparathyroidism (likely to undergo parathyroidectomy in the next 2 years), difficulty controlling serum calcium (likely to require changes in dialysate calcium concentration in the next 2 years), life expectancy < 2 years, prisoners, or inability to give consent.

11. Vulnerable Populations: none

12. Local Number of Participants

Screened: 150 (estimated)

Enrolled: 124

Completed study: 50 (expected)

13. Recruitment Methods

Describe when, where, and how potential participants will be recruited: at dialysis units during dialysis sessions.

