Cognitively Impaired Adults

- Describe the process to determine whether an individual is capable of consent.
Consultation with the attending nephrologist.

Adults Unable to Consent N/A

Waiver or Alteration of Consent Process (consent will not be obtained, required information will not be disclosed, or the research involves deception) N/A

23. Setting

Describe the sites or locations where your research team will conduct the research.

- Identify where your research team will identify and recruit potential participants.
Outpatient dialysis units.
- Identify where research procedures will be performed. Emory Dialysis Centers and Breast Imaging Centers
- Describe the composition and involvement of any community advisory board. N/A.

24. Resources Available

Subject availability. We will need to recruit 62 subjects to ensure a final sample of 50 allowing for 10% drop-out per year (patients dying, receiving kidney transplants, or transferring to other units). This rate has averaged 9.2% among female patients at Emory Dialysis over the past 9 years. Based on our previous data, 60% are expected to have breast arterial calcification, meaning that 103 will need to be recruited and screened for BAC. There are currently 300 female in-center HD patients within Emory Dialysis and it is estimated that at least 80% or 240 will qualify for screening. Therefore, a recruitment rate no greater than 43% will be required.

Timeline. Recruitment completed: 1 month
Last patient started: 2 months
Last patient: 26 months
Data analysis completed: 27 months

Facilities. Emory Dialysis consists of 4 large outpatient dialysis centers distributed around the Atlanta metropolitan region and is staffed by nephrologists, nurse practitioners, registered nurses, and dialysis technicians. The P.I. will work closely with the managers at each unit and hold educational meetings with staff to ensure that they are adequately informed.

The Emory Breast Imaging Center, consisting of several locations, is staffed by Emory radiologists and performs over 20,000 screening mammograms per year. Mammograms are accessible in the Emory Healthcare PACS system and reports are accessible in the Electronic Medical Record. The Center has procedures in place to contact patients about abnormal findings and discuss/arrange additional followup. The P.I. works closely with

the Medical Director ([name]), who is aware of the protocol and will be the sole radiologist interpreting the mammograms.

25. References

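### Section 12's 124 enrolled cannot be reconciled with the 62 starters, 103 screened and 43% recruitment rate in Sections 18 and 24, and no stated input supports it

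*Combined protocol and SAP*

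**What the plan says.** The current protocol gives two participant flows.

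- **Section 18 (Study size, Subject availability).** "The goal is a final cohort of 50". "Using a drop-out rate of 10% per year, a starting sample of 62 will be needed". With 60% of women expected to have BAC, 103 must be screened. Out of 240 women expected to qualify for screening, "a recruitment rate of 43% will be required".
- **Section 24 (Subject availability).** It repeats the 62, 60%, 103 and 240, and ends with "a recruitment rate no greater than 43% will be required".
- **Section 12 (Local Number of Participants).** It lists 150 screened, marked as an estimate; 124 enrolled, with no qualifier; and 50 expected to complete.

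Two other places bear on the comparison. Section 6 fixes the meaning of enrolment: after screening mammography, "those who have BAC will be enrolled". The inclusion criterion in Section 10 agrees. Section 9 sets follow-up at two years per woman. The Section 1 summary gives a sample size of 50.

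**The concern.** Both flows end at 50 completers, but they reach that number through different counts of women screened and started. On Section 6's use of the word, the enrolled count in Section 12 should equal the starting sample in Sections 18 and 24. It is exactly twice as large (124 = 2 x 62), and nothing explains why.

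The enrolment number is a sample-size figure that the ethics committee and the study team rely on. No section says which count closes enrolment, so a coordinator working from Section 12 and one working from Section 18 would stop at different points. The starting number also fixes how many women are asked to take on the dialysate change and the study mammograms, in a trial that Section 16 says offers them no direct benefit. The recruitment rate is the protocol's evidence of feasibility, so a reader needs to know which screening number it describes.

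**Working it through.** **Inputs.** Completers: 50 (Sections 1, 12, 18, 24). Loss: 10% per year (Sections 18, 24) over two years (Section 9), so retention is 0.9 x 0.9 = 0.81. BAC prevalence: 60% (Sections 18, 24). Qualifying pool: 80% of 300 = 240 (Sections 18, 24). Section 12 counts: 150, 124, 50.

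**1. The flow in Sections 18 and 24 reproduces.**
- Starters: 50 / 0.81 = 61.7, rounded up to 62.
- Screened: 62 / 0.60 = 103.3, stated as 103.
- Recruitment rate: 103 / 240 = 42.9%, stated as 43%.

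**2. The flow in Section 12 does not follow from the same inputs.**
- 150 screens x 0.60 = 90 women with BAC, not 124.
- 124 enrolled from 150 screened needs a prevalence of 124 / 150 = 82.7%.
- 124 enrolled at 60% prevalence needs 124 / 0.60 = 207 screens, or 86% of 240.
- 124 starters x 0.81 = 100.4 completers, not 50.
- 50 completers from 124 starters needs a yearly loss of 1 - sqrt(50/124) = 36.5%, against the stated 10%.

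**3. Reading 124 as women consented for screening.**
- 124 x 0.60 = 74.4 starters, and 74.4 x 0.81 = 60.3 completers. These do not match 62 and 50.
- 124 leads to 62 starters only if prevalence is 62 / 124 = 50%. The recruitment rate would then be 124 / 240 = 51.7%.
- Section 10 says that screening is by mammogram, so under this reading Section 12 would also list more women screened (150) than consented to screening (124).

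**4. Screening 150.** This is 150 / 240 = 62.5% of the pool. It would yield 62 starters at a prevalence as low as 62 / 150 = 41.3%.

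**5. Power.** Section 18 uses a standard deviation of 11.9 and a 25% change from 20.1, a difference of 5.025 mm/breast/year. A two-sided paired t-test at 0.05 has 80.9% power with 47 women and 83.3% with 50. The stated 80% for 47 reproduces and does not depend on which flow is used.

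**The case against.** The strongest defence is that the sample-size justification is sound and consistent wherever it is argued: 62, 103 and 43% reproduce, the target of 50 is the same in every section, and 124 appears once with no derivation. On screening, 103 can be the number needed and 150 an allowance; Section 12 marks 150 as an estimate. All of this stands. It removes most of the conflict over screening, but it does not explain 124.

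Three stronger readings are tempting, and the documents do not support them.

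- *A reader might infer that 43% is wrong because 150 / 240 is 62.5%, and that nearly two thirds of qualifying women must therefore agree.* The 43% is the rate needed to screen 103. In Section 24 the pool is at least 240, so 103 divided by it is at most 43%; that is the sense of "a recruitment rate no greater than 43% will be required". It does not cap the number screened, and no section says that 150 must be reached.
- *A reader might infer that twice the justified number of women could be exposed.* At 60% prevalence, 150 screens yield about 90 women with BAC, or 90 / 62 = 1.45 times the starting sample, and then only if enrolment ran past 62. The protocol's own figures do not allow 124.
- *A reader might infer that the final sample size is undefined.* The goal of 50 completers is stated consistently. What is missing is the count at which enrolment closes.

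Nor is this a comparison with superseded text. The revision history records that version 3 raised screening to 150, which may explain why Section 12 differs, but all the conflicting figures stand in the current body of the protocol.

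**Conclusion.** The point holds as an internal inconsistency, not as an arithmetic error. Under the plan's 60% prevalence and 10% yearly loss, 150 screened, 124 enrolled and 50 completing cannot all be true. The enrolled count is twice the justified starting sample, exceeds by 34 the 90 women with BAC that 150 screens would yield, and would leave about 100 completers instead of 50. Reading 124 as consented for screening does not rescue it without a 50% prevalence that the protocol nowhere gives.

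The conclusion assumes that enrolment has the meaning Section 6 gives it, and that yearly loss compounds over two years, as it must to give 62. Why 124 was entered, and whether the expected prevalence has changed, cannot be settled from the documents.

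**What to change.** Use one flow in Sections 12, 18 and 24, by one of two routes.

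1. **If the 60% prevalence still stands:** change the enrolled count in Section 12 from 124 to 62. The 103 and 43% can then remain as the number and rate needed.
2. **If 124 is the number consented for screening:** relabel it so, show 62 as the number starting treatment, and replace the 60%, 103 and 43% in Sections 18 and 24 with the values that flow implies, for example 50% prevalence, 124 screened and 124 / 240 = 52%. Define the 150 as well, so that it does not read as more women screened than consented.

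Under either route, state that 150 is a screening ceiling (up to 62.5% of 240) and that enrolment closes when 62 women with BAC have started.

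The cost is wording in three sections. The stated recruitment rate may become less favourable. No extra patients are needed, and the power statement stays as it is.

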will be stored in the Emory Healthcare PACS system, results of research blood assays will be stored in a password-protected file on a HIPAA-compliant server in the Department of Medicine, and results of clinical assays and dialysis parameters will be stored in the Emory Dialysis electronic medical record. Composite data for final analysis will be stored in a password-protected file on a HIPAA-compliant server in the Department of Medicine. Subjects will be assigned unique identifiers, the key to which will be stored as a separate, password-protected file. Access to all data will be limited to the P.I., coinvestigators, and research coordinator. Any transmitted data will not contain any identifiers. Data will be stored until all primary and secondary analyses are completed.

19. Provisions to Monitor the Data to Ensure the Safety of Participants

Patients will be monitored during each dialysis by nurses or technicians, weekly by nurse practitioners, and monthly by attending nephrologists. Clinical data (pre-dialysis labs and anticoagulation) along with intra-dialytic events are already captured per clinical protocol and stored digitally and will be reviewed monthly by the P.I. Oversight of the progress and safety of the trial will be provided by the PI. Adverse events are not anticipated, but any occurring will be documented and reported according to Emory IRB policies and procedures. Cumulative adverse events and study progress summary will be communicated to the IRB at the time of continuing review.

The only potential safety issue relates to the anticoagulant properties of citrate whereby changing to the non-citrate dialysate may increase the risk of clotting of the dialyzer (already a rare occurrence in the outpatient setting). The staff are already trained to recognize the need to increase the heparin dose prior to clotting and this is already captured on the digital dialysis records, which will be reviewed by the study team on a weekly basis for the first month for each subject. If an increased frequency of clotting or need to increase heparin dosing is noted, subsequent subjects will have their heparin dose increased pre-emptively.

Confidentiality will be protected by utilizing a code number as the only identifier for each subject and the master list will be kept under lock and key with access limited to the PI.

The PI will be responsible for reviewing protocol compliance, data collection and verification.

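### Section 19 ties the weekly record review to each subject's first month and not to the dialysate change, so the return to citrate is missed on any fair reading, and half the switches to non-citrate are missed on a literal one

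*Combined protocol and SAP*

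**What the plan says.** Section 19 names one hazard, and it concerns the dialyzer: "The only potential safety issue relates to the anticoagulant properties of citrate whereby changing to the non-citrate dialysate may increase the risk of clotting". Staff are described as trained to see when more heparin is needed. This is captured in the digital dialysis records, "which will be reviewed by the study team on a weekly basis for the first month for each subject". If clotting or heparin need rises, "subsequent subjects will have their heparin dose increased pre-emptively".

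Section 6 sets the schedule. At the start, "half the patients will continue with citrate dialysis and the other half will be switched to non-citrate dialysis". Then: "After one year, the patients will be switch to the other dialysis". Section 5 gives the background: "Citrasate is the acid concentrate currently in use at all Emory Dialysis units".

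Section 15 says that moving to non-citrate may call for more heparin, because citrate may have some anticoagulant effect. It lists no risk for citrate, on the ground that the units already use it.

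Other monitoring runs throughout. Section 19 states: "Patients will be monitored during each dialysis by nurses or technicians, weekly by nurse practitioners, and monthly by attending nephrologists". Clinical data, including anticoagulation, and intra-dialytic events are "stored digitally and will be reviewed monthly by the P.I".

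**The concern.** The weekly review exists because a change of dialysate may change how much heparin a woman needs. Its timing should therefore follow the change. As worded, it follows the subject. For the women who start on non-citrate, the two coincide at month 0. For the women who start on citrate, they are a year apart.

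The heparin provisions also run in one direction. The protocol provides for raising the dose on non-citrate, reactively or pre-emptively. It has no matching step when citrate, with its possible anticoagulant effect, is resumed. At stake is whether closer study-team oversight falls in the weeks when the heparin requirement is most likely to have shifted.

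**Working it through.** **Inputs**
- Starters: 62 (Sections 18 and 24). The plan's figure reproduces: 50 / 0.90² = 61.7, rounded up to 62.
- Split: half per order (Section 6), 62 / 2 = 31.
- Loss: 10% per year (Section 18), assumed equal in both orders.
- Weekly review: taken as 4 checks per woman per month (assumption).

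**Switches during the study**
- Month 0, citrate to non-citrate: 31
- Month 12, citrate to non-citrate: 31 × 0.90 = 27.9
- Month 12, non-citrate to citrate: 31 × 0.90 = 27.9

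**Coverage of the hazard that the protocol names (change to non-citrate)**

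Switches at risk: 31 + 27.9 = 58.9.

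| Reading of the review window | Switches to non-citrate covered | Month-12 returns to citrate covered |
|---|---|---|
| First study month (literal) | 31 / 58.9 = 53% | 0 of 27.9 |
| First month on non-citrate (contextual) | 58.9 / 58.9 = 100% | 0 of 27.9 |

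Without attrition, the literal figure is 31 / 62 = 50%, and 31 returns are uncovered. No wording supports a third reading, in which the window reopens after every switch.

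**Returns to citrate outside the month-12 count**

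Women who finish on non-citrate at month 24 number about 31 × 0.90² = 31 × 0.81 = 25. Section 14 returns patients to standard care on termination, and at these units that is citrate. Women who withdraw while on non-citrate would go the same way. Their number cannot be derived, because the expected losses are deaths, transplants and transfers (Section 24).

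**Weekly checks**
- Literal plan: 62 × 4 = 248, of which 31 × 4 = 124 fall on citrate-first women with no dialysate change.
- Contextual plan: 58.9 × 4 = 236.
- Review after every in-study switch: (31 + 27.9 + 27.9) × 4 = 86.8 × 4 = 347.
- Extra: 347 − 248 = 99 (literal, with the 124 checks moved to month 12), or 27.9 × 4 = 112 (contextual).

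Section 12 lists 124 enrolled. If all 124 started, every count would double (about 198 to 223 extra checks) and the percentages would not change.

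**The case against.** The strongest reply is that the contextual reading is at least as natural as the literal one. The sentences around the review rule concern the change to non-citrate, Section 5 defines the intervention as the use of non-citrate concentrate, and a month of clotting checks on women whose dialysate has not changed would serve no purpose. This stands. On that reading the named hazard is fully covered and only the return to citrate remains.

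A reader might pool all 86.8 switches and infer coverage of only 31 / 86.8 = 36%, or 58.9 / 86.8 = 68% on the contextual reading. That gives an inferred risk the same weight as the only hazard the protocol names. For the named hazard, the figures are 53% and 100%.

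A reader might also infer that women are unmonitored at month 12. The documents say otherwise: bedside staff, the nurse practitioner, the nephrologist and the monthly P.I. review all continue. Bleeding during dialysis would reasonably fall under intra-dialytic events, and any adverse event is documented and reported. What is lost is weekly rather than monthly study-team review, for one month.

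The pre-emptive heparin rule is a real mitigation for citrate-first women. All women start within about two months (Section 24), so this half reaches non-citrate some ten months or more after the other half did and can benefit from any signal seen. The same rule means that some of them may be on raised heparin when they return to citrate at month 24.

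Finally, these women return to a dialysate they had before the study, in units that use it routinely. Current warfarin users are excluded, and staff may lower heparin unprompted. All of this limits the concern, but none of it supplies a review timed to the return to citrate.

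**Conclusion.** The point holds as a low-severity gap in the timing of targeted oversight. Read literally, the weekly review misses about 28 of 59 switches to non-citrate; read in context, it misses none. On either reading it misses the roughly 28 returns to citrate at month 12. These counts rest on 62 starters, an even split and 10% first-year loss in both orders.

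It would be too strong to say that the protocol exposes women to expected bleeding, or that Section 15's statement on citrate is false. That statement describes citrate as existing care, and excess anticoagulation from a carried-over heparin dose is inferred from Sections 15 and 19. The share of women with raised heparin, the size of the increases and the bleeding risk are not given, so the number affected cannot be estimated. No endpoint, analysis or sample size is affected.

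**What to change.** 1. In Section 19, reword the review window to: *for the first month after each dialysate change, in either direction*. Have the review look for bleeding as well as clotting.
2. Whenever a woman returns to citrate (month 12, end of study at month 24, or withdrawal while on non-citrate), flag any heparin increase made during non-citrate, including a pre-emptive one, to the treating nephrologist before the first citrate session. The dosing decision stays there, since Section 22 says the P.I. does not treat dialysis outpatients.
3. Add to Sections 15 and 19 that heparin may need to be reassessed on return to citrate.

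The cost is protocol wording, the flags, and about 99 to 112 extra weekly checks if 62 women start. If the 124 month-1 checks on citrate-first women are kept rather than moved, the addition is 55.8 × 4 = 223. The records are already captured at every session (Section 6), so no visit or procedure is added. The check counts cover in-study switches only; at month 24 or on withdrawal the flag alone is proposed, because the protocol has no follow-up beyond that point.
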